## **6.10. Previous and Concomitant Therapy**

Medication/therapy will be classified into anatomical therapeutic chemical (ATC) drug classes using the latest version of the World Health Organization (WHO) drug dictionary.

A by-patient listing of previous and concomitant therapy, and a by-patient listing of previous psoriasis therapy will be provided (Analysis population: FAS Population).

### **6.10.1. Previous Therapy**

Previous therapy is defined as the therapy that starts and ends prior to the date of first dose of study treatment in Period 2. If therapy start and/or end dates are missing or partial, the dates will be compared as far as possible with the date of first dose of study treatment in Period 2. If there is clear evidence to suggest that the therapy stopped prior to the first dose of study treatment in Period 2, the therapy will be assumed to be previous only.

The number of patients with the followings will be presented for patients with GPP and EP separately and total (Analysis population: FAS Population):

- Previous therapy (captured in the *Prior Therapy: Indication* eCRF page and *Concomitant Therapy* eCRF page) by WHO ATC Level 4 and WHO drug generic name
- Previous psoriasis therapy (captured in the *Prior Therapy: Indication* eCRF page) by type (topical prescription therapy, topical non-prescription therapy, non-biologic systemic agent, biologic agent, non-biologic non-systemic agent, phototherapy) and therapy. The previous biologic agent will be further classified as TNF- $\alpha$  inhibitor (including infliximab, etanercept, adalimumab, golimumab, certolizumab pegol), interleukin (IL) 12/23 inhibitor (including ustekinumab), IL-17 inhibitor (including secukinumab and brodalumab), and other (including efalizumab, alefacept, or other biological agent).
- Reason for discontinuation of previous psoriasis therapy (captured in the *Prior Therapy: Indication* eCRF page) by type and therapy.

### 6.10.2. Concomitant Therapy

Concomitant therapy for Period 2 is defined as the therapy that starts before, on, or after the first day of study treatment of Period 2 and before the last visit date of Period 2, and continues into Period 2, that is, either no end date (the therapy is ongoing) or an end date on or after the first day of study treatment of Period 2. Concomitant therapy will belong to Period 2 if the therapy starts and ends on the exact same day as the first day of study treatment of Period 2.

Concomitant therapy for Period 3 is defined as the therapy that starts before, on, or after the last visit date of Period 2 and continues into Period 3, that is, either no end date (the therapy is ongoing) or an end date after the last visit date of Period 2. Concomitant therapy will belong to Period 3 if the therapy starts and ends on the exact same day as the last visit date of Period 2.

If a partial medication start date is present, the following imputation rules will be utilized in the analysis:

- If either month or month and day are missing, then use January 1.
- If only day is missing, impute the first day of the month.
- If there is any doubt, the medication will be flagged as concomitant.

The number of patients with the following will be presented for patients with GPP and EP separately and total for Period 2 and for Period 3, respectively (Analysis population: FAS Population for Period 2, Maintenance Dosing Period Population for Period 3):

- Concomitant therapy (captured in the *Concomitant Therapy* eCRF page) by WHO ATC Level 4 and WHO drug generic name.

### 6.11. Efficacy Analyses

[Table RHC.V.6.1](#) includes the description and derivation of the primary and secondary efficacy measures.

Summaries of efficacy measures will be provided in patients with GPP and EP separately for Period 2 and for Combined Periods 2 and 3, respectively (Analysis population: FAS Population for Period 2, Maintenance Dosing Period Population for Combined Periods 2 and 3).

By-patient listings of each efficacy measure will be provided (Analysis population: FAS Population).

**Table RHCV.6.1. Description and Derivation of Primary and Secondary Efficacy Measures**

Measure	Description	Variable	Derivation / Comment	Imputation Approach if with Missing Components
GIS	Global Improvement Score (GIS): will be assessed in the 4 grades by comparing the psoriatic findings: (1) resolved, (2) improved, (3) unchanged, or (4) worsened. The GIS is assessed based on the comparison of the psoriatic findings, sPGA, PASI score, and other evaluations with those at the baseline.	GIS	Range from 1 to 4: resolved (1), improved (2), unchanged (3), or worsened (4)	Single item, missing if missing
sPGA	Static Physician Global Assessment (sPGA): the physician’s global assessment of the patient’s psoriasis lesions at a given time point (European Medicines Agency [EMA] 2004 [WWW]). Plaques are assessed for induration, erythema, and scaling, and an overall rating of psoriasis severity is given using the anchors of clear (0), minimal (1), mild (2), moderate (3), severe (4), or very severe (5).	sPGA score	Range from 0 to 5: clear (0), minimal (1), mild (2), moderate (3), severe (4), or very severe (5).	Single item, missing if missing
		sPGA (0,1)	An sPGA assessed as either 0 or 1, which represents a clinically meaningful response of minimal plaque severity or complete resolution of psoriasis.	Missing if sPGA is missing
		sPGA (0)	An sPGA assessed as 0, which represents a clinically important endpoint indicating complete resolution of psoriasis.	Missing if sPGA is missing

Measure	Description	Variable	Derivation / Comment	Imputation Approach if with Missing Components
PASI	
Psoriasis Area and Severity Index (PASI): combines assessments of the extent of body-surface involvement in 4 anatomical regions (head and neck, trunk, arms, and legs) and the severity of scaling (S), redness (R), and plaque induration/infiltration (thickness, T) in each region, yielding an overall score of 0 for no psoriasis to 72 for the most severe disease (Fredriksson and Pettersson 1978). Severity is rated for each index (R, S, T) on a 0-4 scale (0 for no involvement up to 4 for very severe involvement):
 
0 = none                      1 = slight                      2 = moderate                      3 = severe                      4 = very severe
 
The body is divided into four anatomical regions comprising the head (h), upper extremity (u), trunk (t), and lower extremity (l). In each of these areas, the fraction of total body surface area affected is graded on a 0-6 scale (0 for no involvement; up to 6 for 90% - 100% involvement):
 
0 = 0% (clear)                      1 = >0% to <10%                      2 = 10% to <30%                      3 = 30% to <50%                      4 = 50% to <70%                      5 = 70% to <90%                      6 = 90% to 100%
	PASI score	
The composite PASI score is calculated by multiplying the sum of the individual-severity scores for each area by the weighted area-of-involvement score for that respective area, and then summing the four resulting quantities as follows:  <math display="block">PASI = 0.1(R_h + T_h + S_h)A_h + 0.2(R_u + T_u + S_u)A_u + 0.3(R_t + T_t + S_t)A_t + 0.4(R_l + T_l + S_l)A_l</math>                     Where,                      Rh, Ru, Rt, Rl = redness score of plaques on the head, upper extremity, trunk, and lower extremity, scored 0-4 respectively;                      Th, Tu, Tt, Tl = thickness score of plaques on the head, upper extremity, trunk, and lower extremity, scored 0-4 respectively;                      Sh, Su, St, Sl = scaliness score of plaques on the head, upper extremity, trunk, and lower extremity, scored 0-4 respectively;                      Ah, Au, At, Al = numerical value translation of % area of psoriatic involvement score for the head, upper extremity, trunk, and lower extremity, respectively.                      PASI scores are treated as a continuous score, with 0.1 increments within these values.
	If any individual score is missing, the PASI score will not be calculated, hence missing
	PASI change from baseline	PASI change from baseline	Calculated as: observed PASI – baseline PASI	Missing if baseline or observed value is missing
	PASI percent improvement from baseline	PASI percent improvement from baseline	
Calculated as:
 $Percent\ improvement\ from\ baseline = 100 \times \frac{Baseline\ PASI - Observed\ PASI}{Baseline\ PASI}$ 
If a patient has experienced an improvement, this measure will be positive. If a patient has experienced a worsening in the condition, this measure will be negative.
	Missing if baseline or observed value is missing

Measure	Description	Variable	Derivation / Comment	Imputation Approach if with Missing Components
	The various body regions are weighted to reflect their respective proportion of body surface area.	PASI 75	A clinically meaningful response; at least a 75% improvement in PASI score from baseline	Missing if baseline or observed value is missing
		PASI 90	Higher level of clearance; at least a 90% improvement in PASI score from baseline	Missing if baseline or observed value is missing
		PASI 100	Complete resolution of Ps; a 100% improvement in PASI score from baseline	Missing if baseline or observed value is missing
BSA	Percentage of Body Surface Area (BSA): The investigator will evaluate the percentage involvement of psoriasis on each patient's BSA on a continuous scale from 0% (no involvement) to 100% (full involvement), in which 1% corresponds to the size of the patient's hand (including the palm, fingers, and thumb) (National Psoriasis Foundation [NPF] 2009).	BSA	Collected as a single scale as part of Psoriasis Area and Severity Index eCRF page. Range from 0% to 100%.	Single item, missing if missing
		BSA change from baseline	Calculated as: observed BSA – baseline BSA	Missing if baseline or observed value is missing
PSSI	Psoriasis Scalp Severity Index (PSSI): will be used if the patient has scalp psoriasis at baseline. The scalp will be assessed for erythema (redness), induration (hardness), and desquamation (shedding of skin) and percentage of area affected as follows: Erythema, Induration and Desquamation: 0 = Absent 1 = Slight 2 = Moderate 3 = Severe 4 = Severest Possible Percent of Scalp Involved: 0 = none 1 = <10% 2 = 10 – 29% 3 = 30 – 49%	PSSI score	The PSSI score is a composite score derived from the sum of the scores for erythema, induration and desquamation multiplied by the score for the extent of scalp area involved (percent of scalp involved). The range is 0 to 72.	If any individual score is missing, the PSSI score will not be calculated, hence missing.
		PSSI score change from baseline	Calculated as: observed PSSI – baseline PSSI	Missing if baseline or observed value is missing

Measure	Description	Variable	Derivation / Comment	Imputation Approach if with Missing Components
	4 = 50 – 69% 5 = 70 – 89% 6 = 90 – 100%			
GPP Severity Index	Generalized Pustular Psoriasis (GPP) Severity Index: will be evaluated only for patients with pustular Ps at screening and at baseline according to the Japanese Dermatological Association GPP revised criteria (2010) (Iwatsuki et al. 2010 [WWW]). This is a composite score derived from the sum of scores for assessment of dermal symptoms, systemic symptoms, and laboratory findings (range, 0 to 17).	Assessment of dermal symptoms total score	Assessment of dermal symptoms will be assessed by the score with the area of erythema (on a 0 to 3 scale), area of confluent pustules (on a 0 to 3 scale), and are of skin edema (on a 0 to 3 scale). The total score will be calculated (range, 0 to 9).	If any individual score is missing, the total score will not be calculated, hence missing.
		Systemic symptoms and laboratory findings total score	Systemic symptoms and laboratory findings will be assessed by the score with fever (on a 0 to 2 scale), WBC (on a 0 to 2 scale), C-reactive protein (on a 0 to 2 scale) and Albumin (on a 0 to 2 scale). The total score will be calculated (range, 0 to 8).	If any individual score is missing, the total score will not be calculated, hence missing.
		GPP severity index total score	GPP severity index total score will be calculated by the sum of assessment of dermal symptoms total score and systemic symptoms and laboratory findings total score (range, 0 to 17).	Missing if assessment of dermal symptoms total score or systemic symptoms and laboratory findings total score is missing
		Assessment of dermal symptoms total score change from baseline	Calculated as: observed total score – baseline total score	Missing if baseline or observed value is missing
		Systemic symptoms and laboratory findings total	Calculated as: observed total score – baseline total score	Missing if baseline or observed value is missing

Measure	Description	Variable	Derivation / Comment	Imputation Approach if with Missing Components
		score change from baseline		
		GPP severity index total score change from baseline	Calculated as: observed total score – baseline total score	Missing if baseline or observed value is missing

### **6.11.1. Primary Outcome and Methodology**

The primary analysis is to assess the efficacy of ixekizumab 80 mg Q2W beyond Week 12 in patients with GPP and EP separately, by presenting the number of patients who decreased their GIS by at least 1 point from Week 12 through Week 20 and with  $\leq 2$  of GIS at any visit of Week 14 (Visit 7), Week 16 (Visit 8), Week 18 (Visit 9), Week 20 (Visit 10), or ETV. (Analysis population: Maintenance Dosing Period Population).

### **6.11.2. Additional Analyses of the Primary Outcome**

As an additional analysis of the primary efficacy measure (i.e., GIS), the following endpoint will be summarized descriptively at each scheduled visit for Period 2 and for Combined Periods 2 and 3, respectively (Analysis population: FAS Population for Period 2, Maintenance Dosing Period Population for Combined Periods 2 and 3):

- Number of patients with each GIS grade (1: Resolved, 2: Improved, 3: Unchanged, 4: Worsened).

### **6.11.3. Other Secondary Efficacy Analyses**

For other efficacy measures, the following endpoints will be summarized descriptively at each scheduled visit for Period 2 and for Combined Periods 2 and 3, respectively (Analysis population: FAS Population for Period 2, Maintenance Dosing Period Population for Combined Periods 2 and 3):

- Number of patients who achieve sPGA (0, 1) and sPGA (0)
- Number of patients who achieve PASI 75, PASI 90, and PASI 100 from baseline
- Change from baseline, and percent improvement from baseline in PASI
- Change from baseline in PSSI in patients with scalp involvement at baseline
- Change from baseline in percent of BSA involvement of psoriasis.

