### **6.3.1. Nonresponder Imputation (NRI)**

Categorical binary efficacy and health outcomes variables will be summarized using a nonresponder imputation (NRI) method. Patients will be considered a nonresponder if they do not meet the clinical response criteria or have missing clinical response data at the scheduled time point. All patients who discontinue study treatment at any time prior to the scheduled visit for any reason will be defined as nonresponders regardless of study continuation without study treatment at the visit. Enrolled patients without at least 1 post-baseline observation will also be defined as nonresponders.

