## 6.8. Patient Characteristics

### 6.8.1. Demographics and Baseline Characteristics

The following demographic variables and baseline characteristics will be summarized descriptively for patients with GPP and EP separately and total (Analysis population: FAS Population):

- Age at the time of informed consent (in years): It will be calculated using an imputed date of birth of July 1st in the year of birth collected in the *Demographics* eCRF page as follows:

$$\text{Age (years)} = \frac{\text{Date of informed consent} - \text{Imputed date of birth}}{365.25}$$

- Age group: <65 years, ≥65 years to <75 years, ≥75 years
- Gender
- Race
- Race subcategory: Japanese, other (if “No” is selected for the “Race Asian” collected in the *Demographics* eCRF page)
- Height (cm)
- Weight (kg)
- Weight category: <80 kg, ≥80 kg and <100 kg, ≥100 kg
- Body mass index (BMI) (kg/m^2): It will be calculated as follows:

$$\text{BMI (kg / m}^2\text{)} = \frac{\text{Weight (kg)}}{(\text{Height (m)})^2}$$

- Alcohol use: never, current, former
- Caffeine use: never, current, former
- Tobacco use: never, current, former
- Previous systemic therapy: never used, non-biologic only, biologic only, biologic and non-biologic.
  - Non-biologics are defined as: methotrexate, cyclosporine, retinoids, corticosteroids, fumaric acid derivatives, apremilast, other non-biologics, and psoralen and ultraviolet A (PUVA)
  - Biologics are defined as: efalizumab, ustekinumab, infliximab, etanercept, alefacept, adalimumab, golimumab, certolizumab pegol, secukinumab, brodalumab, or other biologics
- Previous non-biologic systemic therapy: never used, ever used
- Previous biologic therapy: never used, ever used
- Previous phototherapy (ultraviolet B [UVB] or PUVA): never used, ever used
- Previous IL-17 therapy (secukinumab or brodalumab): never used, ever used
- Age at GPP or EP diagnosis (in years)
- Duration since GPP or EP diagnosis (in years): It will be calculated using the date of GPP or EP diagnosis as follows:

*Duration since GPP or EP diagnosis (years)*

$$= \frac{\text{Date of informed consent} - \text{Date of GPP or EP diagnosis}}{365.25}$$

In case of partial date of GPP or EP diagnosis, the following imputation rules will be utilized:

- If both month and day are missing, impute July 1.
- If month is missing and day is not missing, impute July 1.
- If only day is missing, impute 15.
- Psoriasis vulgaris: yes, no
- Psoriatic arthritis: yes, no

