- Baseline sPGA as continuous variable
- Baseline sPGA category: 0, 1, 2, 3, 4, 5
- Baseline PASI score
- Scalp psoriasis: yes, no
- Baseline PSSI score
- Baseline BSA (%)

- Baseline Itch NRS score
- Baseline DLQI total score
- Diagnosis of GPP (GPP only): acute GPP, other
- Type of GPP (GPP only): GPP with preceding psoriasis vulgaris, other: If start date of psoriasis vulgaris is prior to diagnosis date of GPP, it will be classified into GPP with preceding psoriasis vulgaris. Otherwise, it will be classified into other. If start date of psoriasis vulgaris and/or diagnosis date of GPP are missing or partial, these dates will be compared as far as possible. If there is clear evidence to suggest that the psoriasis vulgaris started prior to the diagnosis of GPP, the patient will be assumed to be GPP with preceding psoriasis vulgaris.
- Mutation of IL-36 RN (GPP only): compound heterozygous, heterozygous, homozygous, no mutation, other, unknown
- Baseline assessment of dermal symptoms total score (GPP only): It will be assessed by the score with the area of erythema (on a 0 to 3 scale), area of confluent pustules (on a 0 to 3 scale), and are of skin edema (on a 0 to 3 scale) (see table below). The total score will be calculated (range, 0 to 9).

Assessment of dermal symptoms (0 - 9 points)				
	Severe	Moderate	Mild	None
Area of erythema*	3	2	1	0
Area of erythema with pustules**	3	2	1	0
Area of edema**	3	2	1	0

\*% against body surface area (Severe:  $\geq 75\%$ , Moderate:  $< 75\% \geq 25\%$ , Mild:  $< 25\%$ )

\*\*% against body surface area (Severe:  $\geq 50\%$ , Moderate:  $< 50\% \geq 10\%$ , Mild:  $< 10\%$ )

- Baseline systemic symptoms and laboratory findings total score (GPP only): It will be assessed by the score with body temperature (on a 0 to 2 scale), leucocytes (on a 0 to -2 scale), C-reactive protein (on a 0 to 2 scale) and serum albumin (on a 0 to 2 scale) (see table below). The total score will be calculated (range, 0 to 8).

Systemic symptoms and laboratory findings (0 - 8 points)			
Score	2	1	0
Body temperature ( $^{\circ}\text{C}$ )	$\geq 38.5$	$37 \leq < 38.5$	$< 37$
Leucocytes ( $/\mu\text{L}$ )	$\geq 15,000$	$10,000 \leq < 15,000$	$< 10,000$
C-reactive protein (mg/dl)	$\geq 7.0$	$0.3 \leq < 7.0$	$< 0.3$
Serum albumin (g/dl)	$< 3.0$	$3.0 \leq < 3.8$	$\geq 3.8$

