		DLQI work and school domain	Sum of responses of questions question #7A and #7B: #7A. Has your skin prevented you from working or studying? #7B. If No: how much has your skin been a problem at work or studying?	If the answer to question #7A is missing, this domain is missing. If #7A is No, and #7B is missing, this domain is missing.

Measure	Description	Variable	Derivation / Comment	Imputation Approach if with Missing Components
		DLQI personal relationships domain	Sum of responses of questions #8 and #9: #8. How much has your skin created problems with your partner or any of your close friends or relatives? #9. How much has your skin caused any sexual difficulties?	If one question in a domain is missing, that domain is missing.
		DLQI treatment	Response of question #10: #10. How much of a problem has the treatment for your skin been, for example by making your home messy, or by taking up time?	If one question in a domain is missing, that domain is missing.
		DLQI total score	A DLQI total score is calculated by summing all 10 question responses, and has a range of 0 to 30 (less to more impairment) (Finlay and Khan 1994; Basra et al. 2008).	If two or more questions are missing, the total score is missing. Note: #7B could be a valid missing while #7A is not “No.” That is, #7 should be considered as one question.
		DLQI (0,1)	A DLQI (0,1) response is defined as a post-baseline DLQI total score of 0 or 1. A DLQI total score of 0 to 1 is considered as having no effect on a patient’s HRQoL (Khilji et al. 2002; Hongbo et al. 2005).	Missing if DLQI total score is missing
		DLQI (0)	A DLQI (0) response is defined as a post-baseline DLQI total score of 0.	Missing if DLQI total score is missing
		DLQI total score and domain scores change from baseline	Calculated as: observed DLQI (total score or domain scores) – baseline DLQI (total score or domain scores)	Missing if baseline or observed value is missing

For health outcomes measures, the following endpoints will be summarized descriptively at each scheduled visit for Period 2 and for Combined Periods 2 and 3, respectively (Analysis population: FAS Population for Period 2, Maintenance Dosing Period Population for Combined Periods 2 and 3):

- Change from baseline in Itch NRS score
- Number of patients who achieve Itch NRS  $\geq 4$  point reduction from baseline for patients who had baseline Itch NRS  $\geq 4$

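### The sPGA and DLQI response counts carry no baseline condition, and PASI response has no rule at baseline PASI 0, so a patient who enters at floor can be counted without having improved, or cannot be scored

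*SAP*

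**What the plan says.** **Response rules.** SAP 6.11.3 plans the count "Number of patients who achieve sPGA (0, 1) and sPGA (0" at each scheduled visit, on the FAS Population for Period 2 and on the Maintenance Dosing Period Population for Combined Periods 2 and 3. Table RHCV.6.1 defines the first of these as "An sPGA assessed as either 0 or 1". For quality of life, Table RHCV.6.2 states "A DLQI (0,1) response is defined as a post-baseline DLQI total score of 0 or 1". No baseline value enters either rule.

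**PASI.** Table RHCV.6.1 computes percent improvement by dividing by baseline PASI, on a scale where 0 is a valid score. PASI 75/90/100 are cut-offs on that percentage. The table says what to do when a baseline or observed value is absent, but not when baseline is 0. Under SAP 6.3.1, patients who "have missing clinical response data at the scheduled time point" are nonresponders.

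**Entry.** Protocol 6.1 admits GPP patients on the ministry's diagnostic criteria, at screening and baseline, without a minimum sPGA, PASI or DLQI. EP patients need at least 80% body surface involvement with inflammatory erythema.

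**Baseline tables.** SAP 6.8.1 plans "Baseline sPGA category: 0, 1, 2, 3, 4, 5" and "Psoriasis vulgaris: yes, no". Table RHCV.6.1 describes the sPGA thus: "Plaques are assessed for induration, erythema, and scaling, and an overall rating of psoriasis severity is given". Protocol 9.1.2.2 speaks of the patient's lesions overall.

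**Measures with a baseline condition.** In SAP 6.12 the itch response is a "reduction from baseline for patients who had baseline Itch NRS" of at least 4. In SAP 6.11.3, PSSI is limited to patients with scalp involvement at baseline.

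**The concern.** A count of patients in a given state measures improvement only if nobody starts in that state. Trials usually secure this with an entry floor on the same scale. Here GPP entry has none, and neither the sPGA nor the DLQI count supplies one in the analysis.

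The results are reported by disease, in very small groups and without inference, so the count is the whole result. A patient clear on the sPGA at Week 0 and clear at Week 20 would appear in the achieved column, and a reader would credit the treatment.

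PASI has the opposite gap. At baseline 0 the programmer must choose how to handle a quantity that the SAP does not define. One natural choice puts the patient among the nonresponders of the PASI 75/90/100 tables, while the percent-improvement summary has no value for the same patient. Two tables built on one quantity would then have different denominators, with no explanation in the plan.

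**Working it through.** The plan has no power or sample-size calculation that bears on this point. The 12 patients are a feasibility figure, with at least 5 GPP and 5 EP wanted in Period 3 (SAP 5.2). The check therefore applies the SAP's rules at the boundary values.

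**1. State endpoints with no change from Week 0.** The rules are score ≤1 for (0,1) and score = 0 for (0).

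| Week 0 score, unchanged | (0,1) achieved | (0) achieved |
|---|---|---|
| 0 | yes | yes |
| 1 | yes | no |
| 2 or more | no | no |

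The table holds for sPGA and for the DLQI total. The entry persists only while the score stays at target and the patient remains on treatment with data. Worsening to 2 or more, a missing visit or stopping treatment gives a nonresponse under SAP 6.3.1.

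**2. PASI at baseline 0.** The formula reproduces the stated range: (0.1 + 0.2 + 0.3 + 0.4) × 12 × 6 = 72. Percent improvement is 100 × (B − O)/B, with B baseline and O observed.
- B = 0, O = 0: 0/0, undefined.
- B = 0, O = 2: −200/0, undefined.
- B = 0.1, O = 0: 100%. B = 0.1, O = 0.1: 0%.

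The gap is confined to a baseline of exactly 0. Change from baseline in PASI remains defined there.

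**3. Can EP enter at PASI 0?** Assume that regional areas weigh 10, 20, 30 and 40%, as in PASI, and that redness is at least 1 wherever skin is involved. The lowest score compatible with 80% involvement has a clear head and area grade 5 (just under 90%) in the other three regions. The involved area is then just under 0.9 × 0.9 = 0.81, and PASI is (0.2 + 0.3 + 0.4) × 1 × 5 = 4.5. So PASI 0 can arise only in GPP.

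**4. Size, as an illustration.** Take 5 GPP patients, with 2 responders among those who could improve. Let *m* of the 5 enter with sPGA 0 or 1 and PASI 0, and stay there. The values of *m* are assumed. The PASI column as written treats undefined as missing.

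| *m* | sPGA (0,1) as written | PASI 75 as written | Either, among patients who could improve |
|---|---|---|---|
| 0 | 2/5 (40%) | 2/5 (40%) | 2/5 (40%) |
| 1 | 3/5 (60%) | 2/5 (40%) | 2/4 (50%) |
| 2 | 4/5 (80%) | 2/5 (40%) | 2/3 (67%) |

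**5. Chance of at least one floor patient among 5.** If a share *f* of GPP patients enters at floor, the chance is 1 − (1 − *f*)^5. The documents give no value for *f*. For assumed values of 0.05, 0.10 and 0.20 it is 22.6%, 41.0% and 67.2%. These figures only restate the assumption.

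**The case against.** The strongest reply is that such patients may not exist. GPP criteria must be met at both screening and baseline, and patients must be candidates for phototherapy or systemic therapy. The tabulated sPGA categories are simply the full rating scale, and the psoriasis vulgaris item does not say that erythema is absent at Week 0. If lesions are rated overall, as the protocol has it, GPP erythema would be scored, and redness is a PASI component. A baseline of 0 then becomes implausible. A DLQI of 0 or 1 in active GPP or extensive EP is also conjecture. All of this stands. The point rests on a missing rule, not on a demonstrated patient.

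The precedent is also imperfect. The itch condition is there because a 4-point fall from below 4 is impossible, whereas an sPGA condition would remove patients who already hold the target state. That is fair for sPGA and DLQI. The parallel is direct for PASI, where the response cannot be computed.

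Finally, the baseline summaries and by-patient listings would show any floor patient, and GPP activity has its own index. This limits the harm but does not correct the tabulated count.

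Three stronger readings should be resisted:
- A reader might infer that floor patients are responders whatever happens. Step 1 shows that they are not.
- A reader might infer that baseline PASI 0 is a nonresponse by rule. The SAP never equates undefined with missing.
- A reader might infer that an sPGA response beside a PASI nonresponse is a contradiction. One is a state and the other a relative change, so the two can differ legitimately.

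**Conclusion.** The point holds as a gap in the response definitions. A patient at sPGA or DLQI 0 or 1 at Week 0 who stays there is counted as achieving the endpoint without improving. PASI 75/90/100 and percent improvement have no defined value at baseline PASI 0. The sPGA issue concerns mainly GPP, the PASI issue only GPP, and the DLQI issue either disease.

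Each such patient shifts a count by 1, which is 20 percentage points in a group of 5. The direction is upward for sPGA and DLQI. For PASI the patient stays in the denominator as a nonresponder, provided that undefined is handled as missing. How many patients are affected is unknown and may be none.

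The reach is limited to descriptive secondary endpoints. The primary GIS count does not use these rules. This is a cheap improvement to the plan and does not threaten its main conclusion.

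**What to change.** In SAP 6.11.3 and 6.12, count each response among patients whose baseline leaves room for it:

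- sPGA (0,1): baseline sPGA ≥2
- sPGA (0): baseline sPGA ≥1
- DLQI (0,1): baseline DLQI total ≥2
- DLQI (0): baseline DLQI total ≥1
- PASI percent improvement and PASI 75/90/100: baseline PASI >0

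Print the denominator in each cell and keep the excluded patients in the by-patient listings, so that any worsening among them stays visible. In SAP 6.3.1, add that nonresponder imputation does not apply to a PASI response that is undefined because baseline PASI is 0.

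The cost is a few lines of SAP text and one baseline filter per table, with no new data. Denominators may differ slightly between endpoints, as they already can for itch and PSSI. If nobody enters at floor, the counts do not change.
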